5. ADVERSE EVENTS

5.1. DEFINITIONS

Adverse Event (AE): any untoward medical occurrence in a patient or clinical study subject.

Serious Adverse Event (SAE): any untoward medical occurrence or effect that:

- **Results in death**
- **Is life-threatening** – refers to an event in which the subject was at risk of death at the time of the event; it does not refer to an event which hypothetically might have caused death if it were more severe
- **Requires hospitalisation or prolongation of existing inpatients' hospitalisation**
- **Results in persistent or significant disability or incapacity**
- **Is a congenital anomaly or birth defect**

Medical judgement should be exercised in deciding whether an AE is serious in other situations. Important AEs that are not immediately life-threatening or do not result in death or hospitalisation but may jeopardise the subject or may require intervention to prevent one of the other outcomes listed in the definition above, should also be considered serious.

5.2. REPORTING PROCEDURES

All adverse events should be reported. Depending on the nature of the event the reporting procedures below should be followed. Any questions concerning adverse event reporting should be directed to the Chief Investigator in the first instance.

5.3.1 Non serious AEs

All such events, whether expected or not, should be recorded

5.3.2 Serious AEs

An SAE form should be completed and emailed to the Chief Investigator within 24 hours. However, hospitalisations for elective treatment of a pre-existing condition do not need reporting as SAEs.

All SAEs should be reported to the London- West Research Ethics Committee where in the opinion of the Chief Investigator, the event was:

- 'related', ie resulted from the administration of any of the research procedures; and
- 'unexpected', ie an event that is not listed in the protocol as an expected occurrence

Reports of related and unexpected SAEs should be submitted within 15 days of the Chief Investigator becoming aware of the event, using the NRES SAE form for non-IMP studies. The Chief Investigator must also notify the Sponsor of all related and unexpected SAEs.

Local investigators should report any SAEs as required by their Local Research Ethics Committee, Sponsor and/or Research & Development Office.

Contact details for reporting SAEs

[contact]

CI email (and contact details below)

Please send SAE forms to: [contact]
Tel: **xxx** (Mon to Fri 09.00 – 17.00)

6. ASSESSMENT AND FOLLOW-UP

All candidates will be followed up for 12 months following initial eIPP measurement. The formal end of this study will be 12 months after the eIPP measurement of the 150th incident cohort patient. No further recruitment to the prevalent cohort group will take place after the recruitment of the 150th incident patient. Incidental findings will not be recorded and reported in this study. Only the outcome mentioned in Section 3.2 will be recorded and analysed. Participants will be advised to report incidental findings to their GP and clinical care team as per local guidelines or standard of care.

7. STATISTICS AND DATA ANALYSIS

7.1. POWER CALCULATION

A small underpowered observational study of measured IPP Castellnaos et al(7), observed an event rate of 36% in a group of patient with high IPP compared with 17% in a group with low IPP. Using these estimates (with alpha of 0.05 with a power of 0.8, including a 0% drop out rate) a minimum of 146 patient will be recruited to the incident cohort. A similar number in the prevalent cohort should confirm any findings.

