2. STUDY OBJECTIVES

The primary objective of this research protocol is to investigate whether eIPP is correlated to non-infectious PD-related complications in end-stage renal failure patients.

The secondary objective is to assess the relationship of eIPP with patient-reported outcome measures particularly gastrointestinal symptoms.

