3. STUDY DESIGN

This will be a basic science study involving procedures with human participants. It is a prospective observational study examining a prospective cohort of patients treated with peritoneal dialysis for kidney failure.

This will include two separate cohorts within the study, an incident cohort which will include all patients from the time of PD catheter insertion until 8 weeks after starting PD. A second prevalent cohort will include all patients treated with PD who are greater than 8 weeks from the start of dialysis. Patients will be recruited to either the incident or prevalent cohort.

A minimum of 150 patients will be recruited to both cohorts, so there will be a total of 300 participants.

The study will involve the delivery of two clinical assessments only, the measurements required to estimate IPP and the administration of the gastrointestinal symptom rating scale (GSRS) questionnaire at three time points. Aside from these additional assessments there will be no changes to clinical care and specifically any changes to intra-peritoneal dialysate volume will only be made by the clinical team caring for the patient without reference to the eIPP or GSRS.

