The estimated IPP will be assessed at Visit 1 using the equations included in Appendix 2 with the Li formula used for the primary outcome measure.

For the prevalent and incident cohorts. Visit 1 will take place at the time of study enrolment. Visit 2 will take place alongside a routine clinic visits between 60 to 120 days after enrolment (2-4 months). Visit 3 will similarly take place between 320 and 380 days (11-13 months) after study enrolment.

Participants who refuse to fill in the GSRS questionnaire or

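### Section 7.1 claims 80% power from event rates by measured IPP, but the exposure is estimated IPP; unless the estimate predicts complications in its own right, the design delivers less power than those rates imply

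*Combined protocol and SAP*

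**What the plan says.** Section 7.1 cites one earlier study, "A small underpowered observational study of measured IPP", which "observed an event rate of 36% in a group of patient with high IPP compared with 17% in a group with low IPP". From these rates, "with alpha of 0.05 with a power of 0.8" and "including a 0% drop out rate", it concludes that "a minimum of 146 patient will be recruited to the incident cohort", and adds that a prevalent cohort of similar size should confirm any findings. Section 3 rounds up: "A minimum of 150 patients will be recruited to both cohorts, so there will be a total of 300 participants".

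The exposure is a different quantity. The primary objective in Section 2 is to "investigate whether eIPP is correlated to non-infectious PD-related complications in end-stage renal failure patients". Section 3.1 says that "The estimated IPP will be assessed at Visit 1", and Appendix 1 makes a formula based on waist circumference and trunk depth the primary one. No section provides for measuring IPP. Section 1.1 describes the accuracy of the estimating equations favourably but gives no figure. It also says that the link between eIPP and abdominal complications has not been adequately studied. The data analysis part of Section 7 mentions descriptive statistics only. Sidedness, the eIPP cut-point, the group split and the test are not given.

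**The concern.** The 19-point difference belongs to groups formed by measured pressure. If patients are classified by an imperfect estimate, some with high pressure fall in the low group and some with low pressure in the high group. When the estimation error is unrelated to outcome, each observed rate moves towards the overall rate. Section 7.1 carries the full difference over unchanged, so its 80% describes a study that measures IPP.

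The stake is how a null result would be read. A reader who takes 80% at face value could conclude that an effect of pressure of the size seen in the earlier study had been ruled out, when error in the estimate was a likely alternative explanation.

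**Working it through.** **Inputs from the plan.** p1 = 0.36, p2 = 0.17, difference 0.19, alpha 0.05, power 0.80, no dropout, N = 146 (Section 7.1). **Not in the plan, so assumed:** two-sided test, 1:1 split at the median (mean rate 0.265), and the correlation r between eIPP and measured IPP, taken as 0.7 to 0.9.

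**Step 1: the plan's own figure.** With pooled variance, n per group = [1.96·√(2 × 0.265 × 0.735) + 0.842·√(0.36 × 0.64 + 0.17 × 0.83)]² / 0.19² = (1.223 + 0.513)² / 0.0361 ≈ 83.5. That is 84 per group, 168 in total, not 146. Other two-sided 1:1 methods give 162 (unpooled), 166 (arcsine) and 188 (continuity-corrected). One-sided 1:1 gives 132 (pooled), or 152 with continuity correction. Among the one- and two-sided variants tried, with splits from 1:1 to 1:3, the only one within 3% of 146 is one-sided with twice as many low- as high-pressure patients (48 + 96 = 144). The plan states neither choice.

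**Step 2: power at 146 with perfect agreement.** Power = Φ[(d − 1.96·s0)/s1], where s0 = √(2 × 0.265 × 0.735/73) = 0.0730 and s1 = √((0.36 × 0.64 + 0.17 × 0.83)/73) = 0.0713. This gives Φ[(0.190 − 0.143)/0.0713] = Φ(0.66) = 74.4%. At the planned 150 it is 75.6%.

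**Step 3: replace measured IPP by eIPP.** Take the two as bivariate normal with correlation r, and let eIPP carry no information on risk beyond measured IPP. Two shapes of risk give a range:

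- Risk linear in measured IPP: the difference becomes r × 0.19.
- Risk steps at the median of measured IPP: the difference becomes (2/π)·arcsin(r) × 0.19.

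At r = 0.8 the linear shape gives 0.152 (34.1% vs 18.9%), and power Φ[(0.152 − 0.143)/0.0720] = 55%. The step gives 0.590 × 0.19 = 0.112 (32.1% vs 20.9%), and power Φ[(0.112 − 0.143)/0.0725] = 33%. A log-linear shape calibrated to the same two rates agrees with the linear one within about a point.

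**Step 4: no dichotomy.** Use a logistic model calibrated to 36% above and 17% below the median (slope 0.65 per SD of measured IPP), with eIPP analysed as continuous.

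| r | Difference, linear / step (points) | Power, median split, linear / step | Power, continuous eIPP (approx.) |
|---|---|---|---|
| 1.0 | 19.0 / 19.0 | 74% / 74% | 87% |
| 0.9 | 17.1 / 13.5 | 65% / 46% | 81% |
| 0.8 | 15.2 / 11.2 | 55% / 33% | 73% |
| 0.7 | 13.3 / 9.4 | 44% / 25% | 62% |

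All at N = 146, two-sided 0.05. The last column is approximate: a simple Wald calculation gives 87%, 80%, 71% and 60%.

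**Step 5: the variant nearest to the plan's 146.** One-sided with a 1:2 split at N = 146, power is 80.6% at r = 1.0, 73% (linear) or 56% (step) at 0.9, and 64% or 44% at 0.8. Power falls with r here too.

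**Step 6: drop the assumption on the error.** At r = 0.8 with a step in risk, let the part of eIPP not explained by measured IPP shift risk by plus or minus 10 to 12 points. The rates by measured IPP stay at 36% and 17%, but those by eIPP become about 36% to 37% vs 16% to 17%, and power at 146 is 76% to 83%. The fall in power is therefore conditional.

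**The case against.** **The direction is not guaranteed.** The primary formula uses waist and trunk depth, which might relate to hernia or leak directly, and a pressure reading may itself contain error. Step 6 shows that a direct effect could offset the loss. A reader might infer that power is lower for any imperfect correlation. The documents do not support that without the assumption that estimation error is unrelated to outcome given measured IPP. Equally, they contain nothing to support a direct effect of 10 to 12 points, which is more than half of the whole 19-point difference.

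**Not all of the shortfall comes from estimation.** Under a two-sided 1:1 comparison, about six points (80% to 74%) are gone at r = 1.0. That is a separate defect in the stated sample size, and it must be corrected first.

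**The median split is not in the plan.** Analysed as continuous, eIPP reaches about 80% power at r = 0.9. A reader might take the lowest figures as the power of this study; they rest on a dichotomy and a step in risk that the plan does not state. What stands is that power falls as r falls in the continuous analysis as well.

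**The study asks about eIPP, not about pressure as a cause.** This is correct, and a null result for eIPP answers the stated objective in its own terms. The planning difference is nevertheless borrowed from measured pressure, so the stated power does not apply to that objective.

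**Only descriptive statistics are planned, and the source is already called underpowered.** Neither withdraws the stated alpha and power, which remain the justification for the sample size. Nor does the prevalent cohort settle the matter. The plan presents it as confirmation rather than for pooling, and pooling all 300 by median split at r = 0.8 would give 85% (log-linear) or 60% (step).

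**Conclusion.** The concern holds in conditional form. The 80% in Section 7.1 is computed from rates by measured IPP and applied without adjustment to a study of eIPP. If estimation error is unrelated to outcome given measured IPP, power is below what those rates imply in every analysis examined here. The starting point is about 74% at 146 patients for a two-sided 1:1 comparison.

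The size of the further loss cannot be fixed from the documents, because the correlation, the test and the cut-point are all missing. For assumed correlations of 0.7 to 0.9 it runs from slight (about 81%, continuous, r = 0.9) to severe (25%, step effect, median split, r = 0.7). The direction is firmer than any single number. This affects how the result is read rather than whether the study can proceed.

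**What to change.** In Section 7.1:

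- Say that 36% vs 17% refers to measured IPP.
- Name the comparison, its sidedness and the group split, or say that eIPP will be analysed as continuous.
- Correct the baseline so that the sample size and power agree when r = 1.0. For a two-sided 1:1 comparison, either 146 patients with about 74% power or 168 with 80%.
- Give power for eIPP as a short table over plausible correlations, using the published validation figure for the primary formula if there is one. State the assumption that estimation error is unrelated to outcome given measured IPP.

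In the data analysis part of Section 7, commit to reporting the association of eIPP with complications and its confidence interval. Say that a null result will not be read as excluding an effect of pressure with 80% power.

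The cost is a paragraph and a small table, and the stated power becomes less favourable. Restating it needs no extra patients or procedures. Holding 80% for eIPP would be a separate decision: with a two-sided median split it would take 208 (linear) to 332 (step) patients at r = 0.9.

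### The 146 patients in Section 7.1 do not follow from its printed inputs: a two-sided 0.05 test with equal groups needs 162 to 168, and the planned 150 give about 76-77% power, not 80%

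*Combined protocol and SAP*

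**What the plan says.** Section 7.1 relies on one earlier study of measured intraperitoneal pressure, which "observed an event rate of 36% in a group of patient with high IPP compared with 17% in a group with low IPP". From these rates it sizes the incident cohort: "with alpha of 0.05 with a power of 0.8, including a 0% drop out rate) a minimum of 146 patient will be recruited". On the second cohort it says: "A similar number in the prevalent cohort should confirm any findings".

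Section 3 sets recruitment slightly higher: "A minimum of 150 patients will be recruited to both cohorts, so there will be a total of 300 participants". Section 6 uses the same target: "The formal end of this study will be 12 months after the eIPP measurement of the 150th incident cohort patient".

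The primary objective in Section 2 is to "investigate whether eIPP is correlated to non-infectious PD-related complications in end-stage renal failure patients".

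The document does not state the sidedness of the test, the formula, an eIPP cut-off, or the expected proportions with high and low eIPP. The data analysis text in Sections 7.2 and 7.3 does not supply them, because it plans descriptive statistics only.

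**The concern.** Two event rates, an alpha, a power and a drop-out rate fix the sample size once sidedness and group split are chosen. The usual choices are two-sided and equal groups, and they give a clearly larger number than 146. The usual alternative, one-sided, gives a clearly smaller one.

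This calculation is the only justification given for the size of the incident cohort, and the prevalent cohort borrows it. The 150th incident patient also ends prevalent recruitment and sets the end of the study. If the 80% is not what the design delivers, a null result will be read with more confidence than it deserves. As printed, a reader cannot tell which test the 80% describes.

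**Working it through.** **Inputs.** From Section 7.1: p1 = 0.36, p2 = 0.17, alpha 0.05, power 0.80, drop-out 0%, N = 146. From Sections 3 and 6: N = 150. Not printed, so assumed: equal groups (varied in step 3) and a two-sided test (z = 1.960), with one-sided (z = 1.645) alongside. For 80% power, z = 0.842.

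Derived: d = 0.19, d² = 0.0361; p1(1−p1) + p2(1−p2) = 0.2304 + 0.1411 = 0.3715; mean rate 0.265, so 2 × 0.265 × 0.735 = 0.38955.

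**Step 1. Try to reproduce 146 (n per group).**

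- Unpooled: n = (zα + zβ)² × 0.3715 / 0.0361. Two-sided: 7.849 × 10.291 = 80.8. One-sided: 6.183 × 10.291 = 63.6.
- Pooled: n = (zα√0.38955 + zβ√0.3715)² / 0.0361. Two-sided: (1.2233 + 0.5130)² / 0.0361 = 83.5. One-sided: (1.0266 + 0.5130)² / 0.0361 = 65.7.
- Arcsine: n = 2(zα + zβ)² / h², with h = 2·asin√0.36 − 2·asin√0.17 = 0.437. Two-sided 82.2; one-sided 64.7.
- Continuity-corrected pooled: two-sided 93.7; one-sided 75.8.

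| Formula | Two-sided total | One-sided total |
|---|---|---|
| Unpooled | 162 | 128 |
| Arcsine | 166 | 130 |
| Pooled | 168 | 132 |
| Continuity-corrected | 188 | 152 |

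The stated 146 is not reproduced by any of them.

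**Step 2. Power at the stated and planned sizes, equal groups.** Unpooled power = Φ(d/√(0.3715/n) − zα). Pooled power = Φ((d√n − zα√0.38955)/√0.3715). For n = 75, two-sided: unpooled Φ(2.700 − 1.960) = 77.0%; pooled Φ((1.6454 − 1.2233)/0.6095) = 75.6%. The exact figure enumerates two binomials with the chi-square rejection region.

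| Total | Two-sided pooled | Two-sided unpooled | Two-sided exact | One-sided (pooled to unpooled) |
|---|---|---|---|---|
| 146 | 74.4% | 75.9% | 74.9% | 83.6-84.6% |
| 150 | 75.6% | 77.0% | 76.0% | 84.5-85.4% |

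**Step 3. Could an unequal split help?** With the high-eIPP share varied from 5% to 95%, the best two-sided power is 74.6% (pooled) or 76.5% (unpooled) at 146, and 75.7% or 77.6% at 150. The smallest two-sided total over any split is about 160 (unpooled) or 167 (pooled). If 30% of patients were high-eIPP (an assumption; 45 versus 105), power at 150 falls to 70.7% pooled, 70.9% exact and 65.7% unpooled.

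**Step 4. Could rounding of the printed rates explain it?** Over all rates that round to 36% and 17%, the two-sided total runs from 146 to 182 (unpooled) and from 152 to 188 (pooled). Only the most favourable corner, 36.49% versus 16.5% unpooled, reaches 146.

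**Step 5. What does give a number near 146?**

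- One-sided pooled, inflated by 10%: 66 × 1.1 = 72.6, rounded to 73 per group, total 146.
- One-sided pooled with about 32-33% of patients high-eIPP: about 144 to 147 at 0% loss.
- One-sided test on the log relative risk, equal groups: 73.1 per group, 148 after rounding up.

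The first contradicts the printed 0% drop-out. The other two need a sidedness, and a split or a method, that are not printed.

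**The case against.** The strongest reply is that the test may have been one-sided. Then 150 patients give 84.5-85.4% with equal groups, and the stated 80% is conservative. One-sided 0.05 with 10% inflation lands exactly on 146, and including an allowance of 0% is odd phrasing that could be a misprint for 10%. The rationale in Section 1.2 is also directional: it links high pressure to hernias and leaks.

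Part of this stands. The shortfall in power depends on the two-sided reading, and the one-sided route is a plausible origin of the figure. But it is conjecture. The document prints 0%, says nothing about a one-sided test, and words its objective as a correlation without direction. If this is the origin, two of the inputs are missing or misprinted, and Section 7.1 still needs correcting.

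A second reply is that the effect is small. That is fair. With 17% in the low group, 150 patients give 80% two-sided power at about 37% in the high group (36.8% unpooled, 37.2% pooled) instead of 36%. The rates come from a study that the protocol itself calls small and underpowered, and which measured pressure rather than estimating it. That uncertainty outweighs the arithmetic gap, but it does not make the printed figure right.

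A third reply is that Sections 7.2 and 7.3 plan no hypothesis test, so restating the power leaves a larger gap open. That is true, and it is a separate matter. Finally, a calculated minimum of 146 and a recruitment minimum of 150 are compatible; using one figure is only tidier.

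**Conclusion.** The concern holds. With equal groups and the printed 0% drop-out, the usual formulas for a difference in proportions do not give 146 at either sidedness. Two-sided at 0.05, the requirement is 162 to 168 (188 with continuity correction). Power is 74.4-75.9% at 146 and 75.6-77.0% at 150, so the stated 80% is about 3 to 4 points too high at the planned size, and no group split closes the gap.

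That 146 does not follow from the printed inputs is firm. That power is below 80% rests on the two-sided reading; one-sided, it would be about 84-85%. All these figures assume complete outcome data. Section 3.2 lists several reasons for early withdrawal, and any resulting loss of outcomes would lower them. This should be corrected, but it does not undermine the study.

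**What to change.** In Section 7.1, state the sidedness, the assumed high:low eIPP split, the formula and the drop-out allowance, and restate the power so that it follows from them. The sponsor should first check the original calculation, in particular whether it was one-sided and whether 0% is a misprint.

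If two-sided, suitable wording would be:

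> With 150 incident patients in equal high- and low-eIPP groups, complete follow-up and a two-sided alpha of 0.05, power is about 76% to detect 36% versus 17%. It is lower if the groups are unequal or outcomes are lost.

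If one-sided, say so and give about 84% at 146 or 85% at 150, for equal groups and complete follow-up.

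Two optional edits: use a single figure (146 or 150) throughout, and say that the prevalent cohort will be used to examine whether findings are consistent, its size resting on the same calculation.

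The cost is wording only. No patients are added, and the one downside under the two-sided reading is a slightly less favourable stated power.

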7.2. DATA ANALYSIS

7.3. Descriptive statistics will be used in assessing outcome measures.

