1. INTRODUCTION

1.1. BACKGROUND

Peritoneal dialysis (PD) is a commonly used renal replacement therapy for patients with end-stage renal disease, which accounts for 9% of renal replacement therapy in the world(1). Significantly lower cost, easy technique to learn at home and less nurse training being required make it a competitive alternative to haemodialysis. Despite the advantages, PD is associated with several complications, including peritonitis, catheter malfunction, and dialysate leaks, which can affect the patient's quality of life and survival(2,3). While studies have shown a relationship between intraperitoneal pressure (IPP) and various abdominal complications(4), invasive measurement of IPP, is logistically difficult, such that the practice of regular IPP measurement and with subsequent titration of dialysate volume is only recommended in children(5,6).

There are studies trying to simplify the measurements by calculating an estimated IPP (eIPP) with simple anthropometry measurements(7–10). Although they show good accuracy in estimating the actual IPP, there is a lack of studies to validate the correlation between eIPP and abdominal complications, including patient reported outcomes. The burden of gastrointestinal symptoms is high in patients treated with PD, the association with IPP is unclear but it is conceivable that high IPP may be associated with bloating and early satiety(11,12).

The aim of this research protocol is to investigate the relationship between eIPP and non-infectious abdominal complications in PD patients.

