Appendix 1- Formulas for estimating Intra-Peritoneal Pressure

Given the evidence base the primary outcome is based upon the Li formula.

1) Castellanos formula(7):

$eIPP = 5.820 + 0.462 \times BMI + 0.387 \times \text{Charlson comorbidity index} - 0.096 \times \text{months of PD} - 0.002 \times \text{Daily usual UF}$

2) Scanziani formula(8):

$eIPP = 1.0839 + 0.53 \times BMI + 0.211 \times \text{fill volume (L)}$

3) De Jesús Ventura formula(9):

Fill volume = 2L: $eIPP = -17.4 \times (\text{dialysate volume}/\text{body surface area}) + 38.7$

Fill volume = 2.5L: $eIPP = -11.3 \times (\text{dialysate volume}/\text{body surface area}) + 36.6$

Fill volume = 3L: $eIPP = -8.7 \times (\text{dialysate volume}/\text{body surface area}) + 37.2$

● Body surface area will be calculated by Du Bois formula(15):

■ $0.007184 \times \text{height (cm)}^{0.725} \times \text{weight (kg)}^{0.425}$

4) Li formula(10):

Fill volume = 2L: $eIPP = \text{Waist (cm)} * 0.193 - \text{distance from decubitus plane to mid-axillary line} * 0.907 + 8.613$

Fill volume = 1.5L: $eIPP = \text{waist (cm)} * 0.218 - \text{distance from decubitus plane to mid-axillary line} * 0.850 + 4.127$

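### The analysis plan is descriptive only: it gives no effect measure, test, eIPP scale or cut-off for the association the study was sized to test

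*Combined protocol and SAP*

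**What the plan says.** - **Objective (Section 2).** The primary objective is "to investigate whether eIPP is correlated to non-infectious PD-related complications in end-stage renal failure patients".
- **Sizing (Section 7.1).** A small published study of measured pressure "observed an event rate of 36% in a group of patient with high IPP compared with 17% in a group with low IPP". With alpha 0.05, power 0.8 and 0% dropout, this leads to a minimum of 146 in the incident cohort. Sections 3 and 6 work to 150. For the second cohort: "A similar number in the prevalent cohort should confirm any findings".
- **Analysis (Section 7.2; the sentence itself is numbered 7.3).** In full: "Descriptive statistics will be used in assessing outcome measures".
- **What is fixed.** Section 3.1 sets eIPP at Visit 1, "with the Li formula used for the primary outcome measure", and Appendix 1 agrees: "Given the evidence base the primary outcome is based upon the Li formula". (Section 3.1 points to Appendix 2 for the equations, but they are in Appendix 1.)
- **Outcome (Section 3.2).** A new hernia, pleuroperitoneal fistula (PPF), patent processus vaginalis (PPV) or retroperitoneal leak during the 12 months from enrolment. Data collected before an early withdrawal are to be used.
- **Fill volume.** Appendix 1 prints Li equations for 2 L and 1.5 L only. Section 3.1 records prescribed day and night volumes. Section 3 describes "an incident cohort which will include all patients from the time of PD catheter insertion until 8 weeks after starting PD".

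**The concern.** Alpha and power describe a test, and the plan contains none. Four things are open: whether eIPP is continuous or grouped, where any high/low line falls, how the association is expressed, and what counts as evidence for it. Without a defined result in the incident cohort, the prevalent cohort has nothing definite to confirm.

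Fixing these choices after the outcomes are known would let the data influence them. Two smaller gaps feed into the same analysis. The plan does not say which recorded volume selects the Li equation, or what happens when the volume is absent or is neither 1.5 L nor 2 L. It also keeps data from patients who leave early without saying how those data enter the analysis.

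**Working it through.** **1. The plan's own figure.** Inputs from Section 7.1: p1 = 0.36, p2 = 0.17, alpha 0.05, power 0.8, dropout 0%. Sidedness and group split are not stated; I take two-sided and 1:1. The mean rate is 0.265.

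n per group = [1.96·√(2·0.265·0.735) + 0.8416·√(0.36·0.64 + 0.17·0.83)]² / 0.19² = (1.223 + 0.513)² / 0.0361 = 83.5, so 84 per group and 168 in total.

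One-sided gives 132. The stated 146 is not reproduced from the stated inputs; 132 × 1.10 gives about 146 but contradicts the 0% dropout. Two-sided power at 1:1 is 74.4% with 146 and 75.6% with 150. That is a separate matter, but it shows that sidedness and split are among the unspecified items.

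**2. Power depends on the unstated choice.** Assumptions: 36% and 17% lie either side of the median, and r is the correlation of eIPP with measured pressure. Section 1.1 says of the estimating equations "Although they show good accuracy in estimating the actual IPP", but gives no r.
- Linear truth: logit(p) = −1.113 + 0.653x, with x the measured pressure in SD units. This is solved to give 36% above and 17% below the median; odds ratio per SD = e^0.653 = 1.92.
- Step truth: 36% above the median, 17% below.
- eIPP = r·x + √(1 − r²)·noise.
- N = 146, 6,000 simulated studies: likelihood-ratio test on continuous eIPP against a pooled z test on the median split.

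| r | Linear: continuous / split | Step: continuous / split |
|---|---|---|
| 1.0 | 91% / 74% | 56% / 69% |
| 0.9 | 84% / 65% | 48% / 45% |
| 0.8 | 75% / 54% | 38% / 33–34% |
| 0.7 | 62% / 43% | 30% / 24% |

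If the high group is one third of patients (linear, r = 1), power is about 88% against 68–72%. If it is one quarter, 84–86% against 66–67%. At N = 150 the figures are 0 to 3 points higher.

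**3. Searching for a cut-off.** No true association, event rate 26.5%, nominal 5%: one pre-fixed cut about 5%; best of three about 12%; best of five about 16%; any cut between the 20th and 80th percentiles about 32%.

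**4. Fill volume.** From Appendix 1, the 2 L equation minus the 1.5 L equation = (8.613 − 4.127) + (0.193 − 0.218)·waist − (0.907 − 0.850)·distance = 4.486 − 0.025·waist − 0.057·distance. For assumed waist and distance of 80 and 8 cm this is 2.03; for 95 and 11 cm, 1.48; for 110 and 14 cm, 0.94. The same body gets a different eIPP according to the volume used. If 10%, 20% or 30% had no usable volume and were excluded (assumed; N = 131, 117, 102; linear, continuous), power would be 88%, 84% and 79% at r = 1, and 69%, 65% and 60% at r = 0.8.

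**5. Withdrawal.** Assumed: 20% withdraw, linear truth, r = 1, uniform times.
- Unrelated to eIPP: counting event-free leavers as event-free gives odds ratio 1.89; excluding them, 1.95; Cox regression gives hazard ratio 1.70.
- Log-odds of withdrawal −0.7 or +0.7 per SD of eIPP: event-free 2.04 or 1.70; excluded 1.82 or 2.13; Cox 1.70 in both.
- Null rejection under that linked withdrawal: event-free 6.7% or 6.2%; excluded 7.2% or 6.4%; Cox 4.9% or 4.3%. Cox here assumes that withdrawal is unrelated to event risk given eIPP.

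**The case against.** The study is observational, and describing incidence by eIPP group could be all that was meant. That reading is possible. But it supplies neither the grouping nor any inference, and it leaves the alpha, the power and the confirmatory cohort of Section 7.1 without a purpose.

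The better objection is that continuous regression is a preference. The sizing is high against low, a pre-fixed split follows it more closely, and the split wins when the truth is a step and r is near 1. This stands: what is required is pre-specification, and a split fixed in advance would also close the gap.

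It is also fair that r, the median placement, the share without a usable volume and the withdrawal pattern are all assumed. The existence of the gap depends on none of them.

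A reader might infer three stronger things that the documents do not support:
- That the formula could be chosen after the event. It could not: Li at Visit 1 is fixed.
- That the study carries a false-positive rate of about 32%. Nothing says a cut-off will be searched for; the plan only fails to rule it out.
- That incident patients enrolled before dialysis have no Li value. Section 3.1 records a prescribed volume at Visit 1, and one may exist before dialysis starts. The gap is a missing rule.

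**Conclusion.** The point stands and should be fixed. Followed exactly, the plan yields a description and cannot deliver the test for which the incident cohort was sized. The unmade choice is worth roughly 17 to 21 points of power if log-odds are linear. If the truth is a step, it is worth about 13 points in the other direction at r = 1 and little at lower r.

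With 36% and 17% placed either side of the median, only the continuous analysis under linearity with r of about 0.9 or more reaches 80%; the median split does not reach it in any case shown. These power levels rest on the assumed r, shape and split, so they show how much the choice matters and do not establish the study's actual power.

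**What to change.** Before outcome data are examined, replace the sentence in Section 7.2 with the following.

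- **Primary analysis, incident cohort.** Any new hernia, PPF, PPV or retroperitoneal leak within 12 months of Visit 1, on continuous Visit 1 Li eIPP, unadjusted, with effect per SD, 95% CI and a two-sided 0.05 test. The basic model is logistic regression with an odds ratio.
- **Withdrawal.** Record dates of event, withdrawal, death, transplant and transfer to haemodialysis. If these are available, make Cox regression on continuous eIPP primary, censoring event-free patients at the end of observation. Death, transplant and transfer are competing events; report them by eIPP. If dates cannot be recorded, keep the logistic model with event-free leavers counted as event-free, repeat with them excluded, report withdrawal by eIPP, and state that both are biased if withdrawal is related to eIPP.
- **Exposure.** State whether the day or night volume selects the Li equation. Restrict the primary analysis to patients whose prescribed Visit 1 volume is 1.5 L or 2 L, and report the number excluded. As sensitivity analyses, (a) add patients with no Visit 1 volume, using their first later recorded volume, only if no event preceded it; (b) repeat in all patients with a recorded volume using the Scanziani formula alone, without mixing formulas.
- **Secondary.** A linearity check; a pre-fixed median split that mirrors the sizing; and a model adjusted for sex, polycystic kidney disease, and hernia or abdominal surgery preceding PD. With 146 × 0.265 = 38.7 expected events and four terms (38.7/4 = 9.7 each), keep that model small. It costs about 6 to 10 points of power if the covariates share 20% of eIPP variance (assumed).
- **Confirmation.** Repeat the unadjusted model in the prevalent cohort.

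Cost: a few paragraphs, modest analyst time and a few extra dates. The other variables are already listed in the protocol. Downsides: a linearity assumption that loses power to the split if the truth is a step and r is near 1, and a somewhat smaller primary set if some patients have no usable volume.
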